14.4 Subject Information and Consent

Prior to conducting any study-related procedures, the investigator must obtain informed consent for each subject, in accordance with applicable law. Consent will be documented on a written ICF. The ICF must be approved both by the Sponsor and by the reviewing IRB prior to presenting it to a subject. Each ICF must comply with the ICH GCP Guidelines and applicable regulatory requirements.

Investigators may discuss study availability and the possibility for entry with a potential subject without first obtaining consent. However, informed consent must be obtained and documented prior to initiation of any procedures that are performed solely for the purpose of determining eligibility for research, including withdrawal from current medication(s). The informed consent process should take place under conditions where the subject has adequate time to consider the risks and benefits associated with his/her participation in the study. The investigator or qualified designee must explain to each subject the aims, methods, reasonably anticipated benefits, and potential hazards of the study.

Once appropriate essential information has been provided and fully explained in layman's language to the subject by the investigator (or a qualified designee), the approved ICF will be signed and dated by both the subject and the person obtaining consent (investigator or designee), as well as by any other parties required by the IRB. The subject will receive a copy of the signed ICF; the original will be retained in the study files. The investigator must document the consent interview and place the record in the study files. The investigator shall also maintain a log of all subjects who sign the ICF and indicate if the subject was enrolled into the study or reason for non-enrollment.

14.5 Confidentiality

The investigator must assure that subjects' anonymity will be strictly maintained and that their identities are protected from unauthorized parties. Only subject initials, age, another unique identifier (as allowed by local law) and an identification code will be recorded on any form or biological sample submitted to the Sponsor, IRB, or laboratory. Laboratory specimens must be labeled in such a way as to protect subject identity while allowing the results to be recorded to the proper subject. Refer to specific laboratory instructions (or in accordance with local regulations). NOTE: The investigator must keep a screening log showing codes, names, and addresses for all subjects screened and for all subjects enrolled in the study. Subject data will be processed in accordance with all applicable regulations; some studies may require double-coding of samples.

The investigator agrees that all information received from the Sponsor, including but not limited to the cePolyTregs Investigator's Brochure, this protocol, CRF/eCRF, the study drug, and any other study information, remain the sole and exclusive property of the Sponsor during the conduct of the study and thereafter. This information is not to be disclosed to any third party (except employees or agents directly involved in the conduct of the study or as required by law)

without prior written consent from the Sponsor. The investigator further agrees to take all reasonable precautions to prevent the disclosure by any employee or agent of the study site to any third party or otherwise into the public domain. In compliance with applicable law and/or ICH GCP Guidelines, the investigator will permit the Sponsor's representatives and, when necessary, representatives of the regulatory authorities, direct access to any medical records relevant to the study for verification of study-related procedures and data. Direct access includes examining, analyzing, verifying, and reproducing any records and reports that are important to the evaluation of the study.

Investigators will obtain authorization from the subject to permit access to study-related records, including personal information.

Authorization is required from each subject (e.g., specific permission granted by such individual to a covered entity for the use or disclosure of an individual's protected health information). The investigator and institution must obtain such waiver/authorization in writing from the subject. Valid authorization must meet the implementation specifications under the applicable privacy laws. Authorization may be combined in the ICF (approved by the IRB), or it may be a separate document (approved by the IRB) or provided by the investigator or Sponsor (without IRB approval).

14.6 Study Initiation

Before the study drug can be shipped to the study site and before enrollment can begin, all applicable documentation and approvals as per local regulations must be in place.

The Sponsor or designee will notify the site when they are activated.

14.7 Case Report Forms and Other Study Records

The investigator will comply with the requirements for all assessments and data collection for each subject, as specified in the protocol.

During each subject's visit to the study site, the investigator or qualified designee will record progress notes in the subject's medical record to document all significant observations. At a minimum, these notes will contain the following:

- Documentation of the informed consent process, including any revised consents.
- The date of the visit and the corresponding visit or day in the study schedule.
- General subject status remarks, including any significant medical findings. The severity, frequency, and duration of any AEs and the investigator's assessment of relationship to study drug must also be recorded.
- Any changes in concomitant medications.
- A general reference to the procedures completed.

UCSF	Clinical Study Protocol No. UCSF-cePolyTregs-01	Page 63 of 72
------	---	---------------

In addition, any contact with the subject via telephone or other means that provides significant clinical information will also be documented in the progress notes, as described above.

Data for this study will be captured in electronic eCRFs. Study auditing, data entry, verification and validation, and subsequent analysis will be performed by the Sponsor, or its designees, in accordance with GCPs and established Standard Operating Procedures.

Clinical data (including AEs, concomitant medications, and applicable clinical laboratory data) will be entered into an electronic database. The creation and validation of the database, data entry, validation, and verification will be performed according to 21 CFR part 11 and other applicable local regulations. The data system includes password protection and internal quality checks, such as automatic range checks, to identify data that appear inconsistent, incomplete, or inaccurate.

14.8 Study Monitoring

The Sponsor or designee will assign monitors who will perform monitoring as frequently as necessary and in accordance with ICH GCP.

Source documents and eCRFs will be reviewed at monitoring visits and any findings will be discussed with the investigational staff. The Sponsor expects that at monitoring visits study documents and staff will be available and a suitable space will be provided for review of the study documents. The monitor will meet with the investigator on a regular basis to provide feedback on the conduct of the study.

14.9 Access to Source Documentation

The study may be subject to audit by the Sponsor, its designee, or by regulatory authorities. If such an audit occurs, the investigator must agree to allow access to required subject records. The investigator should notify the Sponsor promptly of regulatory authority audits that are scheduled and must forward copies of any findings or audit reports to the Sponsor promptly.

By signing this protocol, the investigator grants permission to personnel from the Sponsor, its representatives, and appropriate regulatory authorities for on-site monitoring and review of all appropriate study documentation, as well as on-site review of the procedures employed in data collection, where clinically appropriate.

14.10 Study or Study Site Termination

The Sponsor may suspend or stop the study at all centers or at specific study centers due to (but not limited to) the discovery of an unexpected, serious, or unacceptable risk to the subjects enrolled in the study, a decision on the part of the Sponsor to suspend or discontinue development of the product, failure of the investigator to enroll subjects into the study at an acceptable rate, failure of the investigator to comply with regulatory authority or ICH Guidelines, or submission of knowingly false information.

14.11 Protocol Amendments

The investigator will not make any changes to this protocol without the Sponsor's prior written consent and subsequent approval by the IRB. Any permanent change to the protocol, whether an overall change or a change for specific study site(s), must be handled as a protocol amendment. The Sponsor will write any amendment(s). The investigator will submit each amendment to the IRB. However, a protocol change intended to eliminate an apparent immediate hazard to subjects should be implemented immediately, followed by IRB notification within 5 working days.

If the IRB, investigators, and/or Sponsor conclude that the protocol amendment substantially alters the study design and/or increases the potential risk to the subject, the currently approved written ICF will require modification. In such cases, after the approval of the new ICF by the IRB, the investigator will repeat the informed consent process to obtain the subject's signature on the new ICF before permitting continued participation in the study.

If the Sponsor amends the protocol, agreement from the investigator must be obtained. The IRB must be informed of all amendments and give approval. The investigator must promptly send a copy of the approval letter from the IRB to the Sponsor or its designee.

14.12 Protocol Violations/Deviations

This study should be conducted as specified in this protocol. In the event of a significant deviation from the protocol, the investigator or designee will contact the Sponsor or its designee at the earliest possible time to determine the disposition of the subject involved. If necessary, the Sponsor, Medical Monitor, and investigator will decide whether the subject may continue in the study. Such a decision will be documented by the investigator and Sponsor, as appropriate.

14.13 Quality Assurance

Authorized representatives of the Sponsor, a regulatory authority, or IRB may visit the study site to perform audits or inspections, including source data verification. The purpose of any such audit or inspection is to systematically and independently examine all study-related activities and documents to determine whether these activities were conducted, and data were recorded, analyzed, and accurately reported, according to the protocol, ICH GCP guidelines, and any other applicable regulatory requirements.

The investigator should contact the Sponsor immediately if contacted by a regulatory agency about an inspection.

It is important that the investigator and relevant personnel are available during the possible audits or inspections and that sufficient time is devoted to the process.

14.14 Retention of Data

When the study is completed, the investigator must retain the essential documents for as long as needed to comply with regulatory guidelines and Sponsor requirements. The investigator will

UCSF	Clinical Study Protocol No. UCSF-cePolyTregs-01	Page 65 of 72
------	---	---------------

notify the Sponsor prior to moving or destroying any of the study documents. It is the responsibility of the Sponsor to inform the investigator/institution as to when these documents no longer need to be retained. The investigator should take measures to prevent any accidental or premature destruction of these documents.

14.15 Study Report and Publications

A clinical study report will be prepared and submitted to the appropriate regulatory agency or agencies. The Sponsor will ensure that the report meets the standards set out in the ICH Guideline for Structure and Content of Clinical Study Reports (ICH E3). Note that an abbreviated report may be prepared in certain cases.

Investigators in this study may communicate, orally present, or publish in scientific journals or other scholarly media only after written consent has been obtained from the Sponsor.

The investigator will submit to the Sponsor any proposed publication or presentation along with the respective scientific journal or presentation forum at least 60 days before submission of the publication or presentation.

No such communication, presentation, or publication will include the Sponsor's confidential information (see Section [14.5](#)).

The investigator will comply with the Sponsor's request to delete references to its confidential information (other than the study results) in any paper or presentation and agrees to withhold publication or presentation for an additional 60 days in order to obtain patent protection if deemed necessary.

APPENDIX A Ventilator Protocol (modified from ARDSnet)

Controlled modes of ventilation will be required.

Adjust ventilator to achieve a Vt of 6 ml/kg of predicted body weight. At the physician's discretion, tidal volume can be adjusted +/- 2ml/kg.

Predicted body weight is calculated from age, gender, and height (heel to crown) according to the following equations:

Males: PBW (kg) = $50 + 2.3 \times [\text{height (inches)} - 60]$

Females: PBW (kg) = $45.5 + 2.3 \times [\text{height (inches)} - 60]$

APPENDIX B Ventilator Weaning Procedure

Commencement of Weaning (applicable to subjects ventilated invasively or non-invasively)

Subjects will be assessed for the following weaning readiness criteria each day between 0600 and 1000 hours. If a subject's procedure, test, or other extenuating circumstance prevents assessment for these criteria between 0600 and 1000, then the assessment and initiation of subsequent weaning procedures may be delayed for up to 6 hours.

1. At least 12 hours since enrollment in the trial
2. $\text{FiO}_2 \leq 0.40$ and $\text{PEEP} \leq 8 \text{ cm H}_2\text{O}$ or $\text{FiO}_2 \leq 0.50$ and $\text{PEEP} = 5 \text{ cm H}_2\text{O}$
3. Values of both PEEP and $\text{FiO}_2 \leq$ values from previous day
4. Not receiving neuromuscular blocking agents and without neuromuscular blockade
5. Subject exhibiting inspiratory efforts. If no efforts are evident at baseline, ventilator set rate will be decreased to 50% of baseline level for up to 5 minutes to detect inspiratory efforts.
6. Systolic arterial pressure $\geq 90 \text{ mm Hg}$ without vasopressor support ($\leq 5 \mu\text{g/kg/min}$ dopamine or dobutamine will not be considered a vasopressor)

Spontaneous Breathing Trial Procedure and Assessment for Unassisted Breathing

If criteria 1 to 6 above are met, then initiate a trial of up to 120 minutes of spontaneous breathing with $\text{FiO}_2 < 0.5$ using any of the following approaches:

1. Pressure support (PS) $< 5 \text{ cm H}_2\text{O}$, $\text{PEEP} < 5 \text{ cm H}_2\text{O}$
2. CPAP $< 5 \text{ cm H}_2\text{O}$
3. T-piece
4. Tracheostomy mask

The clinical team may decide to change mode during spontaneous breathing (PS = 5, CPAP, tracheostomy mask, or T-piece) at any time during the spontaneous breathing trial.

Monitor for tolerance using the following:

1. $\text{SpO}_2 \geq 90\%$ and / or $\text{PaO}_2 \geq 60 \text{ mm Hg}$
2. Mean spontaneous tidal volume $\geq 4 \text{ ml/kg PBW}$ (if measured)
3. Respiratory Rate $\leq 35 / \text{min}$
4. $\text{pH} \geq 7.30$ (if measured)
5. No respiratory distress (defined as 2 or more of the following):
 - a. Heart rate $\geq 120\%$ of the 0600 rate ($\leq 5 \text{ min}$ at $> 120\%$ may be tolerated)
 - b. Marked use of accessory muscles

- c. Abdominal paradox
- d. Diaphoresis
- e. Marked subjective dyspnea

If any of the goals a. to e. are not met, revert to previous ventilator settings or to PS \geq 10 cm H₂O with Positive End-expiratory Pressure and FiO₂ = previous settings and reassess for weaning the next morning. The subject will be reassessed for weaning the following day.

Decision to remove ventilatory support:

If tolerance criteria for spontaneous breathing trial (a. to e. above) are met for at least 30 minutes, the clinical team may decide to discontinue mechanical ventilation. However, the spontaneous breathing trial can continue for up to 120 minutes if tolerance remains in question.

APPENDIX C Mechanistic Assessments

Assay	Specific Readout	Comparisons
Assays based on flow cytometry and qPCR to detect cePolyTregs in blood of treated subjects	Percent of endogenous CD4 T cells and Treg	% change from baseline among treatment groups and temporal PK information
Assays based on flow cytometry and qPCR to detect cePolyTregs in the Pulmonary tissue (endotracheal aspirate and mini BAL)	Percent of endogenous CD4 T cells and Treg	% change from baseline among treatment groups and temporal PK information
Flow cytometric, genomic and/or proteomic analyses of cells harvested from endotracheal tubes and mini BAL and blood to determine phenotypic changes in immune subsets	Percent of individual immune subset, expression of activation and memory markers	% change from baseline among treatment groups
Flow cytometric, cell culture and expression analyses of cells harvested from endotracheal tubes and mini BAL and blood to determine functional changes in immune subsets	Functional activities of individual immune subset including cytokine production, cytotoxicity and other immune activities	% change from baseline among treatment groups
C-reactive protein and LDH per clinical laboratory standard methods	Concentrations	% change from baseline among treatment groups and temporal biomarker information
d-dimer per clinical laboratory standard methods	Concentrations	% change from baseline among treatment groups and temporal biomarker information
Albumin per clinical laboratory standard methods	Concentrations	% change from baseline among treatment groups
Troponin I per clinical laboratory standard methods	Concentrations	% change from baseline among treatment groups
Assays for inflammatory cytokines/chemokines, e.g. IL-6, IL-12, IFN γ , GM-CSF, TNF α , IP10, MCP-1, MCP3, and MCP-4	Concentrations	% change from baseline among treatment groups
Frequencies and neutralization activities of SARS-CoV-2-specific antibodies	Titer	% change from baseline among treatment groups
Frequencies and effector function of SARS-CoV-2-specific T cell responses	Percentages of CD4 and CD8 T cells that respond to SARS-CoV-2 antigens, effector molecule expression	% change from baseline among treatment groups

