8.1.1 Part 1 (Phase 1)

Part 1 will utilize a standard 3 + 3 design. The initial cePolyTregs dose, route, and regimen for Part 1 is proposed as a single open-label dose of 1×10^8 cells by IV infusion; this initial dose is based on prior data with related products in other indications and is intended to provide a rapid onset of Treg activity at the target organs. The product is expected to have a self-limited duration of subject exposure of approximately 2 weeks. Dose escalation to single IV doses of 2×10^8 and 4×10^8 cells will be undertaken sequentially based on evaluation by a Data Safety Monitoring Board (DSMB). Dose escalation decisions will be based on the required number of subjects in a cohort completing the 7-day dose limiting toxicity (DLT; see Section 8.8.3) assessment period. After the last subject in each cohort has completed the DLT assessment period, the DSMB will conduct a review of all available data (safety and tolerability) from both the current cohort and cumulative data from all cePolyTregs cohorts before determining recommendations for advancement to the next dose level.

Each cohort will initially enroll 3 subjects. If 0 of 3 evaluable subjects experiences a DLT, then advancement to the next cohort may occur. If 1 of 3 subjects experiences a product-related DLT, then additional subjects will be enrolled in the same cohort for a total of up to 6 evaluable subjects. If 1 out of the 6 subjects experiences a product-related DLT, then advancement to the next cohort may occur. If 2 or more subjects in a cohort of up to 6 subjects experience a product-related DLT, no additional subjects will be enrolled in that cohort until a complete evaluation of all available data can be conducted and an opinion can be rendered by the DSMB as to whether the dose has exceeded the maximum tolerated dose (MTD). Based on cumulative safety, tolerability, product manufacturing feasibility, and PD data from all cePolyTregs cohorts, the RP2D will be determined. The cePolyTregs RP2D will include 6 treated subjects.

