8.6.3 Secondary Efficacy Endpoints

Part 2 (Phase 2a):

Efficacy of cePolyTregs compared with placebo/SOC, as assessed by:

- The proportion of subjects with a 2-point or greater improvement in the WHO severity scale for COVID-19 pulmonary syndrome on each of Study Days 7, 14, 21, and 28
- The proportion of subjects with improvement in the WHO severity scale for COVID-19 pulmonary syndrome to Grade 3 or less on each of Study Days 7, 14, 21, and 28
- The proportion of subjects requiring mechanical ventilation on each of Study Days 7, 14, 21 and 28
- Number of days free of mechanical ventilation on Days 29 and 57
- Mean and median Sequential Organ Failure [SOFA] scores on each of Study Days 7, 14, 21 and 28
- Change in chest imaging (radiograph or CT scan) abnormalities
- All-cause mortality on Study Days 29 and 84

Parts 1 and 2:

Pharmacodynamic and biomarker changes associated with administration of cePolyTregs compared with placebo/SOC, including but not limited to:

- Change from baseline in circulating cePolyTregs
- Change from baseline in pulmonary cePolyTregs by endotracheal aspirate and mini BAL

UCSF	Clinical Study Protocol No. UCSF-cePolyTregs-01	Page 35 of 72
------	---	---------------

- Change from baseline in ferritin, C-reactive protein, LDH, and high-sensitivity troponin I (hs-TnI)
- Change from baseline in d-dimer
- Change from baseline in absolute lymphocyte count
- Change from baseline in C3, C4, and CH50
- Change from baseline in inflammatory cytokines/chemokines, e.g. IL-6, IL-12, IFN γ , TNF α , MCP-1 and MCP-4
- Phenotypic and functional changes from baseline in immune subsets using cytometric, genomic and/or proteomic analyses of cells harvested from endotracheal tubes, mini BAL, and blood

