11.10 Clinical Laboratory Tests

Blood and urine samples will be collected according to the SOE and below. All laboratory tests will be performed at the local laboratory. Samples will be collected pre-dose on Day 0 as per SOE. Repeat laboratory testing will not be required if a test was already performed within the specified time window for collection. Samples may be analyzed for the tests outlined in this protocol and for any additional tests (with the Sponsor's approval) necessary to further evaluate subject safety. These may include, but are not limited to, investigation of unexpected results. Subjects will be in a seated, semi-recumbent, or supine position during blood collection. Collection procedures are described in the study Laboratory Manual.

Table 3 presents the clinical laboratory assessments to be performed.

Table 3. Clinical Laboratory Parameters

Chemistry	Hematology	Urinalysis	Viral Studies

 Sodium Potassium Chloride Bicarbonate Calcium Magnesium Phosphorus Glucose BUN Creatinine Total protein Albumin Uric acid LDH Total bilirubin Direct bilirubin Indirect bilirubin Alkaline phosphatase ALT AST GGT 	
 RBC count Hgb Hct Platelet count WBC count with differential: neutrophils, lymphocytes including absolute CD4 and CD8 count, monocytes, eosinophils, and basophils (absolute counts and percentages) 	
 Appearance Color Specific gravity pH Blood Protein Glucose Bilirubin Urobilinogen Leukocyte esterase Nitrite 
Microscopic analysis:
 
 WBC RBC Epithelial cells Bacteria Casts and/or crystals^a 	
 Anti-HIV Ab HBsAg Anti-HCV Ab (if positive, HCV RNA will be measured) 
Other
 
 Urine pregnancy test^b Ferritin C-reactive protein d-dimer high-sensitivity troponin

Abbreviations: ALT = alanine aminotransferase; AST (SGOT) = aspartate aminotransferase; BUN = blood urea nitrogen; GGT = gamma-glutamyl transferase; HBsAg = hepatitis B surface antigen; Hct = hematocrit; HCV = hepatitis C virus; Hgb = hemoglobin; HIV = human immunodeficiency virus; LDH = lactate dehydrogenase; RBC = red blood cell; RNA = ribonucleic acid; WBC = white blood cell

^a Microscopic analysis of urine should only be performed if clinically indicated.

^b Pregnancy testing only for women of childbearing potential.

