13.7 Pharmacodynamic Analyses

All PD data summaries will use the PD population.

Detailed PD analyses are outlined in [Appendix C Mechanistic Assessments](#).

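### Circulating cePolyTregs are read out only as a percent of the recipient's own CD4 T cells and Tregs, so a shift in that denominator can distort the persistence curve and dose comparisons; add cells per µL alongside

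*Combined protocol and SAP*

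**What the plan says.** Appendix C describes "Assays based on flow cytometry and qPCR to detect cePolyTregs in blood of treated subjects". The specific readout is "Percent of endogenous CD4 T cells and Treg", and the planned comparison is percent "change from baseline among treatment groups and temporal PK information". The soluble markers in the same table are read as concentrations.

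The endpoint in section 8.6.3 is "Change from baseline in circulating cePolyTregs", without a unit; Table 4 (section 11.11) lists the same item under PK markers, also without a unit. Section 13.7 adds no unit: "Detailed PD analyses are outlined in" Appendix C. No section plans cePolyTregs per µL or a conversion to it.

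Table 3 (section 11.10) includes "lymphocytes including absolute CD4 and CD8 count" in the hematology panel. Section 8.6.3 also lists "Change from baseline in absolute lymphocyte count" as a separate endpoint. On persistence, section 8.1.1 says: "The product is expected to have a self-limited duration of subject exposure of approximately 2 weeks". Section 8.7 states that Part 1 data, including the Table 4 biomarkers, inform the RP2D.

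**The concern.** A percent of endogenous cells answers a relative question: how large is the infused population beside the recipient's own? Persistence and exposure by dose are questions about number. The two agree only while the denominator is stable over time and similar between the groups compared.

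The plan gives no assurance of either. Lymphocyte count and immune-subset changes are themselves outcomes. Eligibility (section 9.2) sets floors for white cells and neutrophils but none for lymphocytes, so starting counts may vary widely. Part 1 enrolls 3 to 6 subjects per dose, sequentially and without randomization, so an imbalance in CD4 count between cohorts is plausible and will not average out. Section 8.4.1 also expects some infused cells to proliferate in the recipient; a rising percent cannot tell that from a fall in endogenous CD4 cells.

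At stake are the reading of the blood time course against the expected 2 weeks, and one of the inputs to dose selection.

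**Working it through.** The plan states no figure for this readout, so there is none to reproduce. The check is ratio arithmetic on assumed CD4 changes.

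**Inputs.** From the documents: planned doses of 1, 2 and 4 × 10^8 cells, so adjacent steps are 2-fold (section 8.1.1), and expected exposure of about 2 weeks (same section). Assumed: endogenous CD4 changes by a factor k of 1.5 to 3 over 14 days; CD4 counts differ 2-fold between cohorts; exposure is proportional to dose.

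**Notation.** A = cePolyTregs per µL, E = endogenous CD4 per µL, percent = 100 × A/E.

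**1. Constant infused-cell count.** If E rises k-fold and A does not change, the percent is multiplied by 1/k.

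| k | Change in percent |
|---|---|
| 1.5 | −33% |
| 2 | −50% |
| 3 | −67% |

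Example: 10 cells/µL reads 100 × 10/200 = 5.0% at E = 200 and 100 × 10/600 = 1.67% at E = 600. If E falls, the error reverses: a halving of E doubles the percent.

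**2. Apparent half-life.** With exponential change, the decay rate of the percent is ln 2/h + ln k/14, where h is the true half-life in days. The apparent half-life is ln 2 divided by that rate.

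| True half-life | k = 1.5 | k = 2 | k = 3 |
|---|---|---|---|
| 7 days | 5.4 | 4.7 | 3.9 |
| 14 days | 8.8 | 7.0 | 5.4 |

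**3. Dose comparison.** For a true 2-fold exposure difference, the ratio of percents is 2/r, where r is the CD4 count of the higher-dose cohort divided by that of the lower. For r = 2 it is 1.0, for r = 1 it is 2.0, and for r = 0.5 it is 4.0. The distortion can be as large as the planned dose step.

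**4. Conversion.** A local CD4 count T includes infused CD4+ cells, so T = E + A. With f = A/E, T = E(1 + f), and so A = T × f/(1 + f).
- T = 210, f = 0.05: 210 × 0.05/1.05 = 10.0 per µL.
- T = 610, f = 10/600: 610 × 0.016667/1.016667 = 10.0 per µL.

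Both recover the true count. The simpler product T × f gives 10.5 in the first case, which is 5% too high, and the error grows with f.

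**5. Availability and pairing.** In section 5.2, mechanistic whole blood falls on Days 0, 0.5, 4, 7, 14, 21, 28, 56 and 84, and hematology is scheduled on all of them. Section 11.10 waives a repeat test if one was done within the visit window, and windows run to ±2 days, so a count and a mechanistic sample may be up to 4 days apart. Under the growth rate in step 2, a gap of d days leaves an error factor of k^(d/14):

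| Gap | k = 1.5 | k = 2 | k = 3 |
|---|---|---|---|
| 2 days | 1.06 | 1.10 | 1.17 |
| 4 days | 1.12 | 1.22 | 1.37 |

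This is smaller than the 1.5- to 3-fold distortion removed, but large enough to need a pairing rule.

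**The case against.** A reader might infer that the results will be misread as lymphopenia resolves. The documents do not support that: they never mention lymphopenia, give no CD4 value and state no direction of change. Listing lymphocyte count as a marker shows that it may move, not that it will.

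Nor is the blood curve the only evidence on persistence. Table 4 also lists pulmonary cePolyTregs and sequencing of their expansion. Once the cells are gone, both units read zero, so a detected/not-detected conclusion is much less affected than a half-life, except near the assay limit.

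Nor does this readout decide the RP2D. The synopsis defines the RP2D by PD effect, using markers that may include those in Table 4, where circulating cells stand under PK in a section headed exploratory. They are one possible input, although section 8.6.3 also makes them a secondary endpoint.

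The percent has its own justification. Earlier PolyTregs tracking was reported as a percentage of circulating Tregs (section 7.4), and section 7.2.2 cites the ratio of Tregs to effector T cells as a risk indicator in ARDS. It should stay.

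Finally, the synopsis defers PD and biomarker analysis details to a SAP before database lock, the counts are already collected, and comparisons across cohorts of 3 to 6 remain imprecise in any unit. All of that stands. It makes the correction easy and limits what it can deliver, but it leaves Appendix C as the only current specification, with a unit that does not measure cell number.

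**Conclusion.** The point holds as a risk of distortion, not as a certainty. Followed as written, Appendix C yields a blood PK curve in which infused-cell number and endogenous CD4 count cannot be separated. The sizes above (a 33% to 67% fall with no cell loss; a 2-fold exposure difference hidden or doubled) rest wholly on the assumed CD4 changes and imbalance. With a stable, balanced denominator the distortion would vanish. The primary efficacy analysis and the sample size do not depend on this readout. The change is worth making because the readout is a secondary endpoint that may inform dose selection and the data that correct it are already scheduled.

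**What to change.** In Appendix C and the SAP:

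- Add absolute cePolyTregs per µL as a blood PK readout, reported alongside the percent of CD4 and of Treg.
- Define it as T × f/(1 + f), where f is the ratio of cePolyTregs to endogenous CD4 cells and T is the total absolute CD4 count from Table 3.
- Take T from the draw made with the mechanistic sample or, failing that, the closest in time within a stated pairing window. State how samples without a count inside that window are handled.
- Convert the SARS-CoV-2-reactive CD4 and CD8 percentages to absolute numbers from the matching parent count. Convert other immune subsets only where a parent count is collected; CD4 and CD8 counts cannot convert subsets with a different parent population.

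**Cost.** A short wording change, with no new sample or assay. Local-laboratory counts must be merged with the mechanistic data, and counts from up to 12 centers add between-laboratory variation, which is a further reason to keep the percent beside the absolute value.
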